6.9.4 Anemia

Anemia is an AESI (refer to IB) and important identified risk for bintrafusp alfa. Notably, there are many reasons for anemia in patients with advanced cancer, therefore a thorough investigation of new anemia cases of unspecified etiology is requested.

For new anemia events, items queried may include, but are not limited to, detailed relevant past medical and treatment history, bruising tendency, history of blood transfusions and/or dependency,

and a request for an updated eCRF including details such as concomitant medications, all laboratory data, updated dosing information and, recent tumor evaluation scans.

General guidance for anemia management and evaluation:

1. Participants must enter the study with Hgb values at least 9 g/dL; routine blood test parameters are required in the SoA (see [Table 1](#))
2. All relevant hematologic testing for anemias should be done prior to a blood transfusion, if clinically feasible.
3. Transfusion should be performed at the discretion of the Investigator based on clinical assessment and considered when the participant experiences significant anemia. An attempt should be made to initiate work-up (as specified below) for the cause of anemia prior to transfusion, if clinically feasible, to not confound this work-up. In general, blood transfusions and erythroid growth factors are permitted as clinically indicated.

Guidance for evaluation of suspected anemias is provided in [Table 6](#).

Table 6 Evaluation Guidance of Suspected Anemia Adverse Events

Baseline Anemia Evaluation (Prior to Transfusion, if feasible)	
CBC with differential (e.g., Hgb, hematocrit, MCV, reticulocytes counts, ANC). Peripheral blood smear for cell morphological assessment. Complete metabolic panel including liver panel-LFTs, bilirubin, LDH, renal function, and other chemistries if indicated: 
 1. Coagulation factors (PT, PTT, INR) 2. Urinalysis including culture 3. Iron panel (TIBC, ferritin, Fe) 4. Serum folate, B12 values 5. TSH/hormonal panel 6. Fecal-occult blood testing 7. Erythropoietin. 	
Further Recommendation Based on Suspected Etiology (in Addition to Baseline Anemia Testing)	
Unknown etiology, suspect possible hemolysis	Coombs test, fibrinogen, haptoglobin, d-dimer. Consider hematology consultation. Consider blood transfusion at clinical discretion.
Unknown etiology, suspect possible bleeding	Consider blood transfusion at clinical discretion. Consider surgical/interventional radiology consultation. Consider imaging, as clinically indicated (e.g., FAST scan, CT scan, MRI, angiography). Consider endoscopy (upper/lower).
Unknown etiology despite above work-up	Hematology consultation. Consider bone marrow aspiration/morphologic evaluation.
ANC=absolute neutrophil count, CBC=complete blood count, CT=computed tomography, FAST=Focused assessment with sonography for trauma, Hgb=hemoglobin, INR=international normalized ratio, LDH=lactate dehydrogenase, LFT=liver function test, MCV=mean corpuscular volume, MRI=magnetic resonance imaging, PT=prothrombin time, PTT=partial thromboplastin time, TIBC=total iron binding capacity, TSH=thyroid-stimulating hormone.	

6.9.5 Bleeding Events

Bleeding events are AESIs and considered an important identified risk for bintrafusp alfa (refer to the IB).

6.9.5.1 Mucosal/Non-Tumor Bleeding

Participants treated with bintrafusp alfa were commonly reported with mild to moderate mucosal AEs such as epistaxis, hemoptysis, gingival bleeding and hematuria. In general, these reactions resolve without discontinuation of treatment.

For Grade 2 non-tumor bleeding, see Section 6.8 for general management of Grade 2 treatment-related TEAEs.

For Grade 3 non-tumor bleeding, study treatment must be permanently discontinued unless an alternative explanation can be identified (such as concomitant use of antithrombotic agents, traumatic event, etc.). In case of alternative explanations for the Grade 3 bleeding event, study treatment should be held until the event recovers to Grade ≤ 1 .

For Grade 4 non-tumor bleeding, treatment must be permanently discontinued if no alternative explanation is identified.

6.9.5.2 Tumor Bleeding

Participants treated with bintrafusp alfa were reported in lower frequencies, with Grade ≥ 3 hemorrhages including tumor bleeding. For Grade ≥ 2 tumor bleeding, study treatment must be held until the event recovers to Grade ≤ 1 . Treatment should be permanently discontinued if the Investigator considers the participant to be at risk for additional severe bleeding.

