6.8 Special Precautions

Any treatment-emergent adverse event (TEAE) that is assessed as potentially related to bintrafusp alfa, may require permanent or transient discontinuation of bintrafusp alfa treatment.

Single laboratory values out of the normal range that do not have any clinical correlation do not necessarily need treatment interruption. Questions or concerns with regard to management and/or follow-up of TEAEs should be discussed with the Medical Monitor.

Immune-related AEs, IRRs including hypersensitivity, anemia, TGF- β inhibition mediated skin reactions, and bleeding events are managed and followed up in their respective sections as indicated below. Permanent study intervention discontinuation may be recommended, so the relevant section must be reviewed:

- For suspected irAEs, general management by NCI-CTCAE v5.0 toxicity grading is listed in Section 6.9.2. Recommended guidance and management for specific irAEs as per published guidelines is provided in [Appendix 5](#).
- Infusion-related reaction (IRR) and hypersensitivity reaction guidance are presented in Section 6.9.1.
- Anemia guidance is presented in Section 6.9.4.
- Potential TGF- β -mediated skin AEs guidance and management are provided in Section 6.9.3.
- For guidance and management of bleeding events, see Section 6.9.5.

General guidance:

- In any case, if ≥ 2 doses are missed due to AE, the Medical Monitor should be consulted
- Inability to reduce corticosteroid dose to 10 mg or less of prednisone or equivalent per day within 12 weeks is an indication for permanent treatment discontinuation (except for use of steroids as hormone substitution)
- Persistent Grade 2 or 3 adverse reactions (excluding endocrinopathies controlled with hormone replacement therapy) that do not recover to Grade 0 to 1 within 12 weeks after last dose of study intervention is an indication for permanent treatment discontinuation.

In general, the following applies for TEAEs related to bintrafusp alfa that are not covered by the recommendations for irAE management in [Appendix 5](#):

Grade 4 treatment-related TEAEs

Any Grade 4 treatment-related TEAEs require permanent treatment discontinuation, except:

- Endocrinopathies that have been controlled by hormone replacement

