- Isolated laboratory values out of normal range that do not have any clinical correlation. Discuss with Medical Monitor regarding work-up, management, and treatment continuation versus hold versus discontinuation for isolated Grade 4 laboratory abnormalities
- If alternative explanation is identified for Grade 4 non-tumor bleeding.

See [Appendix 5](#) for guidance on specific Grade 4 irAEs, as most require permanent treatment discontinuation.

Grade 3 treatment-related TEAE

1. Participants with any severe or Grade 3 treatment-related adverse reactions that recur should be permanently discontinued. Exceptions may be considered for the following after discussion with Medical Monitor:
 - Transient Grade 3 flu-like symptoms or fever that is controlled with medical management

- Transient Grade 3 fatigue, local reactions, headache, nausea, emesis that resolves to \leq Grade 1 or baseline
 - Tumor flare phenomenon defined as local pain, irritation, or rash localized at sites of known or suspected tumors
 - Any Grade \geq 3 drug-related amylase or lipase abnormality that is not associated with symptoms or clinical manifestations of pancreatitis
 - Grade 3 Hgb decrease (< 8.0 g/dL) that is clinically manageable with blood transfusions or erythroid growth factor use
 - Increases in ECOG PS \geq 3 that resolves to \leq 2 by Day 1 of the next infusion (i.e., infusions should not be given if the ECOG PS is \geq 3 on the day of treatment and should be delayed until ECOG PS \leq 2)
 - Keratoacanthoma (KA) and cutaneous squamous cell carcinoma (cSCC)
 - Grade 3 non-tumor bleeding requiring intervention or hospitalization if alternative explanation can be identified (such as concomitant use of antithrombotic agents, traumatic event, etc.).
2. See [Appendix 5](#) for guidance on specific Grade 3 irAEs as many require permanent treatment discontinuation, including pneumonitis and nephritis.
 - AST or ALT $>$ 5 times ULN or total bilirubin greater than 3 times ULN must be permanently discontinued, except for participants with liver metastases (for example) who begin treatment with Grade 2 AST or ALT. These participants should be discontinued if AST or ALT increases by \geq 50% relative to baseline and lasts for at least 1 week.
 3. Persistent Grade 3 adverse reactions (excluding endocrinopathies controlled with hormone replacement therapy) that do not recover to Grade 0 to 1 within 12 weeks after dose of treatment.

Grade 2 treatment-related TEAE

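### Sections 6.8 and 6.9.5.2 give different stopping rules for treatment-related Grade 4 tumor bleeding, and for recurrent treatment-related Grade 3 tumor bleeding, with no statement of which prevails

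*Protocol*

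**What the plan says.** Protocol Section 6.8 sets general rules by grade, introduced by "In general, the following applies for TEAEs related to bintrafusp alfa that are not covered by the recommendations for irAE management in" and then a reference to Appendix 5.

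- **Grade 4:** "Any Grade 4 treatment-related TEAEs require permanent treatment discontinuation, except" for three listed items. The only item about bleeding reads "If alternative explanation is identified for Grade 4 non-tumor bleeding". Tumor bleeding is not listed.
- **Grade 3:** "Participants with any severe or Grade 3 treatment-related adverse reactions that recur should be permanently discontinued". The exceptions to this are introduced by "Exceptions may be considered for the following after discussion with Medical Monitor", and the bleeding item among them is again non-tumor bleeding with an alternative explanation.

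Protocol Section 6.9.5.2 deals with tumor bleeding separately. For Grade 2 or higher "tumor bleeding, study treatment must be held until the event recovers to Grade" 1 or less. It then adds: "Treatment should be permanently discontinued if the Investigator considers the participant to be at risk for additional severe bleeding".

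Protocol Section 6.9.5.1 covers non-tumor bleeding. It states: "For Grade 3 non-tumor bleeding, study treatment must be permanently discontinued unless an alternative explanation can be identified". If there is an alternative explanation, treatment is held until Grade 1 or less.

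Section 6.8 refers the reader to 6.9.5 for bleeding, and Section 7.1 points to both 6.8 and 6.9 for events that require withdrawal. SAP Section 15.2.3.5 plans a summary of bleeding events leading to permanent treatment discontinuation.

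**The concern.** Section 6.9.5 classes bleeding as an adverse event of special interest and an important identified risk, and 6.9.5.2 itself reports that Grade 3 or higher hemorrhages, including tumor bleeding, have been seen on the drug. Grade 4 means life-threatening under Appendix 4. For such an event related to treatment, a site that reads 6.8 finds a mandatory stop set by grade. A site that reads 6.9.5.2 finds a hold, with the permanent stop left to judgment.

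Two things are at stake. One is patient safety: whether dosing may restart after a life-threatening tumor bleed depends on the section consulted. The other is interpretation: the count of bleeding events leading to permanent discontinuation would mix the drug's effect with the site's reading of the protocol.

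**Working it through.** No sample size, error rate or event count enters here, so there is no arithmetic and no figure in the plan to reproduce. The check sets the rules side by side, by bleeding type, grade, relatedness and recurrence.

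| Event | Section 6.8 | Section 6.9.5 | Result |
|---|---|---|---|
| Grade 4 tumor, treatment-related | Permanent stop; no exception applies | Hold to Grade 1 or less; permanent stop on Investigator judgment (6.9.5.2) | Conflict |
| Grade 4 tumor, not treatment-related | Grade 4 rule does not apply | As above (6.9.5.2) | One rule |
| Grade 3 tumor, treatment-related, recurrent | Should be permanently discontinued; tumor bleeding is not among the exceptions | As above (6.9.5.2) | Mismatch |
| Grade 3 non-tumor, first event, unexplained | Stop is triggered by recurrence only | Permanent stop (6.9.5.1) | Different triggers; following 6.9.5.1 breaches neither |
| Grade 3 non-tumor, recurrent, with alternative explanation | Exception possible after Medical Monitor discussion | Hold to Grade 1 or less; no Medical Monitor step stated (6.9.5.1) | Different procedure; both can be followed |
| Grade 4 non-tumor | Stop unless there is an alternative explanation | Same (6.9.5.1) | Agree |

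The remaining question is whether the documents settle the first and third rows by giving one section precedence.

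1. The scope sentence of 6.8 sets aside only events covered by Appendix 5. That appendix has no bleeding table, so bleeding stays within the general rules.
2. The exception lists in 6.8 deal with bleeding themselves, at both Grade 3 and Grade 4, and each names non-tumor bleeding only. The natural inference is that tumor bleeding was left under the general rule.
3. Section 6.8 sends the reader to 6.9.5, and 6.9.5.1 sends the reader back to 6.8 for Grade 2 non-tumor bleeding. The sections are written to be read together.
4. Section 7.1 cites both for mandatory withdrawal and ranks neither.

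No statement of precedence was found.

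**The case against.** The strongest reply is that the specific section governs the general one. Section 6.8 does more than cross-refer: it says that bleeding, with the other events of special interest, is managed in its own section and that this section must be reviewed. The grade rules that follow are only introduced as general. Section 6.9.5 calls 6.8 back in where it wants it, for Grade 2 non-tumor bleeding, and does not do so for tumor bleeding. This is a reasonable reading, but it leaves unexplained why the Grade 3 and Grade 4 exceptions in 6.8 mention bleeding at all, and why they exempt only the non-tumor kind. The protocol nowhere states the reading.

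A second reply is that the sections are cumulative. A permanent stop for a related Grade 4 tumor bleed breaches neither section, and 6.9.5.2 contains no explicit instruction to resume. That is correct, and it limits the point: the conflict bites when a site restarts after recovery, which the hold in 6.9.5.2 allows and the Grade 4 rule in 6.8 forbids. It also means that a reader should not infer that two sites taking opposite actions would both comply with the whole protocol. On the cumulative reading the site that restarts does not.

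A third reply is that the SAP output concerned is one descriptive line in a single-arm study, with no test depending on it. That also stands. The main reason to act is the instruction to sites.

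**Conclusion.** The point holds for treatment-related Grade 4 tumor bleeding and, in the same way, for recurrent treatment-related Grade 3 tumor bleeding. It rests on two readings: that the 6.8 rules apply to bleeding because only Appendix 5 events are set aside, and that Grade 2 or higher in 6.9.5.2 includes Grades 3 and 4.

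Broader readings are tempting but not supported:

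- **Every Grade 4 tumor bleed is affected.** The 6.8 rule covers treatment-related events only. A bleed judged unrelated falls under 6.9.5.2 alone.
- **Section 6.9.5.2 is simply hold and resume.** It also contains a permanent stop on Investigator judgment.
- **The Grade 3 non-tumor rules contradict each other.** The triggers differ, but a site that follows 6.9.5.1 breaches neither section. This is a lesser inconsistency; its practical risk is that a site reading only 6.8 misses the stop after a first unexplained event.
- **Grade 4 non-tumor bleeding has a weaker rule than Grade 3.** The two sections agree on the stop. For an explained Grade 4 event they are silent on a hold, which is a gap and not a conflict.

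The size cannot be put as a number of participants. The documents give no rate for these events; 6.9.5.2 describes the frequency only as lower. Any percentage applied to the 135 planned participants would have no basis in the text. The clarification matters for as long as anyone is still being dosed, and the documents do not say how many are. Under SAP Section 6.1, the restricted analysis for the abbreviated report still includes events leading to discontinuation and events of special interest, so the effect on interpretation remains.

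**What to change.** Reconcile Sections 6.8 and 6.9.5.2 so that treatment-related Grade 3 tumor bleeding (first and recurrent) and treatment-related Grade 4 tumor bleeding each lead to one action. Add a sentence to 6.8 stating which section prevails for bleeding events. A short table by bleeding type, grade, relatedness, recurrence and alternative explanation would do this. It could also align the Grade 3 non-tumor triggers and the Medical Monitor step, and fill the gap on a hold for explained Grade 4 non-tumor bleeding. Which actions go into the table is for the sponsor's clinical team; this review takes no position.

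The cost is a protocol clarification and a letter to sites. No procedures, visits or data items are added. If bleeding events have already been handled under the present text, the report should say that the two sections differed when it presents bleeding events leading to permanent discontinuation.

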6.9.6 Other Potential Risks

6.9.6.1 Impaired Wound Healing

Impaired wound healing is considered an important potential risk (a theoretical risk-based on literature findings) for bintrafusp alfa, given the role of TGF- β in wound healing. Management should be discussed with the Medical Monitor for participants requiring surgery on study. It is recommended to hold study intervention for approximately 4 weeks post major surgery for observation. Postoperative wound healing will be closely monitored.

6.9.6.2 Embryofetal Toxicity

Embryofetal toxicities are a known risk of the PD-1/PD-L1 targeting class and are considered important potential risks for bintrafusp alfa. Animal models link the PD-1/PD-L1 signaling pathway with maintenance of pregnancy through induction of maternal immune tolerance to fetal tissue. Embryofetal toxicity is an important potential risk of bintrafusp alfa. An appropriate contraception warning is provided as part of the inclusion criteria. Pregnant and breastfeeding

women are not allowed in the bintrafusp alfa study, and adequate contraceptive measures are recommended during the study to minimize or eliminate the potential risk to the developing fetus.

Respective safety measures comprise inclusion/exclusion criteria for participation in clinical studies with bintrafusp alfa, guidance for prevention, monitoring, and medical management of potential risks, as well as guidance on study intervention interruption or discontinuation.

7 Discontinuation of Study Intervention and Participant Discontinuation/Withdrawal

7.1 Discontinuation of Study Intervention

Participants may be discontinued from study intervention for any of the following reasons, one reinitiating course of treatment may be allowed (see Section 7.1.2.1).

- A participant may discontinue from the study intervention at any time at his/her own request (i.e., withdrawal of consent), and without giving a reason.
- Occurrence of an exclusion criterion, which is clinically relevant and affects the participant's safety, if discontinuation is considered necessary by the Investigator and/or Sponsor.
- A participant may be discontinued at any time at the discretion of the Investigator for safety, behavioral, compliance, or administrative reasons (See Section 6.8 and 6.9 for TEAEs and AESIs that require treatment discontinuation).
- Confirmed PD per RECIST 1.1, with the exception that participants receiving treatment may continue past PD if the participant's ECOG PS has remained at least stable, and if in the opinion of the Investigator, the participant will benefit from continued treatment (See Section 7.1.3).
- Unacceptable toxicity.
- Some TEAEs and AESIs require withdrawal from treatment. See Section 6.8 and 6.9 for additional details.
- Drug must not be given to a known pregnant participant (refer to Appendix 3).
- Use of a prohibited concomitant drug, as defined in Section 6.5.2, where the predefined consequence is withdrawal from the study intervention.

The SoA specifies the data to collect at study intervention discontinuation and follow-up and any additional evaluations that need to be completed.

In case of discontinuation from the study intervention:

- The day of End-of-Treatment will correspond to the day of withdrawal (or within 7 days).
- An attempt should be made to perform all assessments scheduled for the End-of-Treatment visit if possible. If not possible, the most clinically relevant assessments and appropriate eCRFs for the End-of-Treatment visit should be prioritized as feasible.
- Participants will be asked to continue Safety and Survival Follow-up, which includes the collection of data on survival, patient-reported outcome (PRO) questionnaires, and subsequent

anticancer therapy. After completion of the follow-up period or after the End-of-Treatment visit, whichever is applicable, the appropriate eCRF section for Study Termination must be completed.

- If the participant is enrolled into a new study or any new therapy post-withdrawal from study intervention, the Safety Follow-up visit should be scheduled prior to the start of the new treatment irrespective of the 28-day Safety Follow-up period.

7.1.1 Temporary Discontinuation

See Sections 6.8 and 6.9 for guidance on temporary discontinuation from study intervention.

7.1.2 Rechallenge

7.1.2.1 Reinitiation

One reinitiating course of treatment at the same dose and schedule and treatment duration up to 24 months is allowed at the discretion of the Investigator and agreement of the Medical Responsible for:

- Participants who are experiencing SD, a PR, or CR at the time of discontinuation, and then subsequently develop disease progression after stopping therapy, but prior to the End of the Study.

OR

- Participants who are discontinued due to an AE that is subsequently well managed or resolved after stopping therapy, but prior to the End of the Study.

The participant should reinitiate treatment at the treatment phase visit where they left off according to the SoA (see Table 1). Participants who reinitiate treatment should stay on study and should be treated and monitored according the SoA for the rest of the study.

Prior to reinitiation, the Investigator will need to confirm that the benefit of reinitiating treatment outweighs any risk involved, such as that which led to initial treatment discontinuation. For participants with only stable disease at the time of discontinuation, the Investigator should confirm that no other reasonable treatment options are available. In addition, to be eligible for reinitiation, the participant must not have previously withdrawn consent for this trial and should have been followed up with regular eCRF documented evaluation scans up to reinitiation of treatment.

A rebaseline scan must be performed prior to reinitiation of study treatment. Additionally, relevant safety laboratory assessments, including both full hematology and full chemistry results within 2 weeks, must be available and verified. The clinical Investigator will determine whether additional evaluation and work-up are required on a case-by-case basis. A discussion with the study team is warranted to determine whether PK/CCI testing is indicated upon restarting treatment.

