
IRR=infusion-related reactions, IV=intravenous, NCI-CTCAE=National Cancer Institute-Common Terminology Criteria for Adverse Event, NSAIDs=nonsteroidal anti-inflammatory drugs. Once the bintrafusp alfa infusion is interrupted or rate reduced to 50% of previous infusion rate, it must remain decreased for all subsequent infusions. For Grade 3 or 4 IRRs, bintrafusp alfa discontinuation is mandated. For all types and grades of infusion reactions, details about drug physical constitution, method of preparation, and infusion must be recorded.
	

In the event of a Grade 2 IRR that does not improve or worsens after implementation of the treatment modifications indicated in [Table 5](#) (including reducing the infusion rate by 50%), the Investigator may consider treatment with corticosteroids and the infusion should be stopped for that day. At the next infusion, the Investigator may consider the addition of H2 blocker antihistamines (e.g., famotidine or ranitidine), in addition to the above provided recommended optional premedication regimen, for selected participants. However, prophylactic steroids are not permitted. At the next dose, if the participant has a second IRR Grade ≥ 2 on the slower infusion

rate, with the addition of further medication to premedication, the infusion should be stopped, and the Investigator may consider withdrawal of this participant from the study.

Hypersensitivity Reaction

If a hypersensitivity reaction occurs, the participant must be treated according to the best available medical practice. A complete guideline for the emergency treatment of anaphylactic reactions according to the Working Group of the Resuscitation Council United Kingdom and can be found at <https://www.resus.org.uk/pages/reaction.pdf>. Participants should be instructed to report any delayed reactions to the Investigator immediately.

Symptoms may include, but are not limited to:

- Impaired airway
- Decreased oxygen saturation (< 92%)
- Confusion
- Lethargy
- Hypotension
- Pale/clammy skin
- Cyanosis.

Management of hypersensitivity includes:

- Epinephrine injection and IV dexamethasone
- Participant should be placed on cardiac, blood pressure, heart rate, and oxygen saturation monitoring immediately
- Alert intensive care unit for possible transfer if required.

Prophylaxis of Flu-like Symptoms:

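### The reinitiation rule in Protocol 7.1.2.1 does not exclude adverse-event stops that 6.8, 6.9 and Appendix 5 call permanent

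*Protocol*

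**What the plan says.** **Reinitiation.** Protocol 7.1 introduces its list of reasons for stopping with the remark that "one reinitiating course of treatment may be allowed", and points to 7.1.2.1. That section offers one course, which "is allowed at the discretion of the Investigator and agreement of the Medical Responsible for" two groups. The first had stable disease or a response when they stopped and later progressed. The second is "Participants who are discontinued due to an AE that is subsequently well managed or resolved after stopping therapy". Before a restart, "the Investigator will need to confirm that the benefit of reinitiating treatment outweighs any risk involved, such as that which led to initial treatment discontinuation". The section also requires that consent was never withdrawn, that scans continued and were documented, that a new baseline scan is done, and that recent laboratory results are checked.

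**Permanent stops.** Section 6.8 says "Any Grade 4 treatment-related TEAEs require permanent treatment discontinuation, except" in three listed situations. The same section makes recurrent Grade 3 related reactions and defined AST, ALT or bilirubin elevations permanent stops. Section 6.9.2 requires permanent discontinuation for a named list of Grade 4 immune-related events, and the opening of Appendix 5 presents that requirement as a critical instruction. Section 6.9.5.1 says "For Grade 3 non-tumor bleeding, study treatment must be permanently discontinued unless an alternative explanation can be identified", with a parallel rule for Grade 4.

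**Mandated stop.** The footnote to Table 5 in 6.9.1 says "For Grade 3 or 4 IRRs, bintrafusp alfa discontinuation is mandated".

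**The concern.** A participant stopped under one of the permanent rules has, in plain terms, been discontinued because of an adverse event. If the event later settles, she fits the second group in 7.1.2.1. One part of the protocol then says treatment is over, and another says a further course may be considered. Nothing in the text says which prevails.

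What is at stake is participant safety and consistent conduct. Two sites could handle identical cases differently and both cite the protocol. The rules in question include ones that Appendix 5 describes as critical and attributes to FDA recommendations.

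**Working it through.** No figure is involved. The check sets each expressly permanent rule against the adverse-event route in 7.1.2.1 and looks for anything that resolves the overlap.

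| Rule | Exceptions it lists | General exception for later resolution? | Refers to 7.1.2.1? |
|---|---|---|---|
| 6.8, Grade 4 related events not covered by Appendix 5 | Endocrinopathy controlled by hormone replacement; isolated laboratory values; bleeding with another explanation | No | No |
| 6.8, recurrent Grade 3 related reactions | A list to discuss with the Medical Monitor, including some transient symptoms that settle | No, only for those named items | No |
| 6.8, liver-test elevations | Liver metastases with Grade 2 AST or ALT at start | No | No |
| 6.9.2 and Appendix 5, named Grade 4 immune-related events | Conditions for lymphopenia, including failure to resolve within 14 days | No, only for lymphopenia | No |
| 6.9.5.1, Grade 3 and 4 non-tumor bleeding | Another explanation for the bleed | No | No |

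Four observations follow.

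1. **Resolution is written in where it was meant to count.** The recurrent Grade 3 rule excuses certain transient symptoms that settle, and the lymphopenia rule has a 14-day limit. The other rows have no such term.
2. **The adverse-event group in 7.1.2.1 is not just temporary holds.** Those have their own section, 7.1.1, which sends the reader to 6.8 and 6.9.
3. **Section 7.1.2.1 contains exclusions, but not this one.** Prior withdrawal of consent bars a restart, and so does a lack of documented scans. A permanent stop is not mentioned.
4. **A precedence clause appears elsewhere.** For treatment beyond progression, 7.1.3.2 says that meeting any other withdrawal criterion ends treatment. Section 7.1.2.1 has no counterpart.

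A further example comes from the general guidance in 6.8. A Grade 2 or 3 reaction that has not recovered to Grade 0 or 1 within 12 weeks of the last dose is an indication for permanent discontinuation. If it recovers after week 12, the participant falls into the eligible group in 7.1.2.1.

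Appendix 5 does not settle what permanent means for rechallenge. Its Guillain-Barré table makes Grade 3-4 a permanent stop and then advises caution with rechallenge in severe cases. The myositis table makes Grade 4 permanent and then gives similar advice.

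**The case against.** The best counter-argument is that the sections can be read together. Section 7.1.2.1 is permissive, while 6.8 and 6.9 are specific to events, and 7.1 refers to them twice for events that require stopping. The adverse-event group still has content if permanent stops are left out, because 7.1 allows discretionary stops for safety and 6.9.1 lets the Investigator consider withdrawal after a second Grade 2 or higher infusion reaction. The approval and benefit-risk steps are real safeguards. This may well be what was intended, but no sentence says so. The benefit-risk step also expressly weighs the risk that caused the stop, which turns a required permanent stop into a case-by-case judgment.

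A reader might infer several stronger points that the documents do not support:

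- **That anyone with a resolved event may restart.** The conditions in 7.1.2.1 rule out automatic access. Only the eligible category is unrestricted.
- **That 7.1 grants reinitiation after every listed reason.** Its opening only points to 7.1.2.1. The list includes withdrawal of consent, which 7.1.2.1 treats as a bar.
- **That a Grade 3 infusion reaction is a permanent stop.** The footnote says mandated, not permanent.
- **That every Grade 4 immune-related event is a permanent stop.** The Grade 4 rule in 6.8 does not cover events handled in Appendix 5. Section 6.9.2 makes permanence mandatory only for named events. Appendix 5 allows a hold or a discussion of resumption for, among others, Grade 3-4 hypothyroidism, aseptic meningitis and encephalitis.
- **That rechallenge events are lost in the safety summaries.** The SAP does include reinitiation data in the summaries (9.11, 15.1), but this is a declared rule for all reinitiated participants. It flags reinitiation-phase events and lists all adverse events for these participants (15.1, 15.1.1), and it lists their reason for stopping (10.1).

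**Conclusion.** The contradiction holds for stops that the protocol expressly calls permanent: the rows of the table above. For those, 7.1.2.1 followed as written places a participant in an eligible category that another section closes. This is a conflict between stated rules, not only missing detail. For Grade 3 or 4 infusion reactions the position is unclear rather than contradictory.

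In size, it touches each participant stopped under one of these rules whose event later settles or is brought under control before the end of the study. The documents give no basis for a number, and nothing shows that any such participant would meet the other conditions for a restart. The conclusion assumes that discontinuation due to an adverse event in 7.1.2.1 has its ordinary meaning, which includes required stops. No view is taken on which clinical rule should prevail.

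**What to change.** Reconcile 7.1 and 7.1.2.1 with 6.8, 6.9 and Appendix 5. State in 7.1.2.1, with cross-references, whether participants stopped under a rule labelled permanent or mandated are eligible for reinitiation, and align the opening of 7.1 with that statement. Clarify in the same text how the infusion-reaction footnote in Table 5 is to be classed, and whether the rechallenge remarks in Appendix 5 apply after a permanent stop. The sponsor's clinical team decides which passage governs.

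The main cost is one sentence with cross-references, in an amendment or clarification letter. No change to the sample size or the SAP follows from it.
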